This trial reflects one aim (Aim 4) within a larger program of research covered in the IRB application that began with development of the gaming system (Aims 1-2) and initial pilot testing of the gaming self-management approach (Aim 3). Only Aim 4 of the IRB application relates to the multi-site randomized controlled trial. Only the sections of the IRB pertaining to the randomized controlled trial are included here to avoid confusion. Study-related treatment materials that were open-sourced to an internet repository referenced within the published protocol are also included within this document.

The trial is registered at Clinicaltrials.gov NCT02631850.

Dates of IRB Approvals and Associated Modifications:

11/23/15 – IRB Amendment Approved for Aim 4 of the Study (the Multi-site Randomized Controlled trial presented in this original journal article).

9/20/16 – New recruitment flyers were added based on stakeholder revisions to the text on the original recruitment materials and design edits by The Ohio State University's (OSU) Center for Clinical and Translational Sciences.

3/9/17 – Non-significant risk device determination was added for the Recovery Rapids gaming system and the smart-watch app to provide feedback on amount of daily arm use.

5/3/17 – A qualitative survey on experience with CI therapy, especially the behavioral techniques, was added to the post-treatment testing session if the participant consented to an additional interview with the research assistant. This measure was only administered to a small subset of participants at OSU.

Research Protocol

Title A low-cost virtual reality gaming platform for neurorehabilitation of hemiparesis

I. Objectives

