A relatively recent rehabilitation strategy, constraint-induced movement therapy (CI therapy), produces substantial recovery of arm function. Although viewed as the "gold standard" intervention for arm hemiparesis by many practitioners, CI therapy is unavailable to most patients due to its cost, travel/scheduling demands, and dearth of trained providers. For example, CI therapy is typically not covered by insurance and the 30+ hours of assessment and physical training usually cost patients upwards of \$6,000. Most patients are required to travel long distances, often out of state, multiple times a week to seek this care. Many of these patients have only intermittent access to transportation and/or limited financial means to travel. Thus, patient dissatisfaction with not receiving adequate rehabilitation is high and there is a fundamental need for low-cost, accessible interventions with the potential to improve arm function. The objective of this project is to test, in collaboration with the patients it is designed to serve, a home-based, computer-gaming version of CI therapy that will provide high-quality rehabilitation to patients who are typically not afforded access to effective therapies.

Aim 4: A larger randomized controlled trial will be conducted, comparing the effectiveness of a 3D video game delivery model of CI therapy versus traditional clinic-based CI therapy and standard care.

Our team's long-term goal is to use newly available technological innovations to increase access to motor rehabilitation while reducing cost of care. In keeping with our overall program of research, the proposed work aims to establish the comparative effectiveness of a three-dimensional (3D) video game delivery model of CI therapy versus traditional clinic-based CI therapy and standard care. Data from this trial will enable individuals with hemiparesis to evaluate whether a home-based video game therapy has the potential to meet their rehabilitation goals compared to clinic-based CI therapy and traditional rehabilitation approaches. We propose a multisite randomized controlled trial with two subaims:

Aim 4a: To determine the comparative effectiveness of a therapist-as-consultant video-game delivery model of CI therapy. The Motor Activity Log (a reliable and valid measure of arm use for daily activities) and the Wolf Motor Function Test (measures time required to perform functional movements) will serve as primary motor outcome measures.

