Individuals with chronic stroke will be randomized to one of four different interventions: (1) traditional clinic-based CI therapy (35 therapist/client contact hours), (2) therapist-as-consultant virtual reality CI therapy (5 therapist/client contact hours in the clinic and 15 hours of independent game play at home), (3) therapist-as-consultant virtual reality CI therapy with additional therapist contact via telerehabilitation (5 therapist/client contact hours in the clinic, 6 additional brief teleconference sessions, and 15 hours of independent game play in the home), and (4) 5 hours of standard occupational therapy. The clinic-based CI therapy arm is the "gold standard" against which gaming therapy is compared (group 1 versus group 2 and group 3). The comparison to standard care (group 2 versus group 4) will demonstrate whether game-based treatment between therapy sessions enhances motor outcomes. The comparison between groups 2 and group 3 will determine the extent to which additional therapist monitoring via video conference improves treatment response of a home-based intervention. Motor function (Wolf Motor Function Test) and daily use of the more affected hand (accelerometry) will be measured prior to treatment, after treatment, and 6 months later.

Sample & Inclusion/Exclusion Criteria

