Relatively relaxed enrollment criteria will be employed to include a representative sample of patients with upper extremity motor impairment. Patients who have experienced a stroke (of any etiology) resulting in hemiparesis at least six months prior, have preserved ability to comprehend and participate in basic elements of the therapy, who have corrected vision of at least 20/70 (individuals with low vision would have difficulty participating in the gaming intervention), who are not currently participating in other experimental upper extremity trials, who are not currently engaged in other outpatient rehabilitation for their upper extremity, and who have not received Botox within the last 3 months (confound) will be eligible to participate. Eligible participants will receive an in-person screening to ensure their ability to safely engage in rehabilitation. Patients deemed too frail to undergo intensive rehabilitation or those with serious, uncontrolled medical problems will be excluded (e.g., debilitating pain). The recruited sample will represent approximately 50% of individuals with hemiparesis. Participants will be stratified by severity of impairment (see table below) and separately randomized to reduce potential baseline inequality between groups.

Severity of	Shoulder	Elbow	Wrist	Fingers	Thumb
Impairment					
Mild-	Flexion ≥45° and	Extension ≥20°	Extension ≥20°	Extension of all	Extension or
moderate	Abduction ≥45°	from a 90° flexed	from fully flexed	MCP and (PIP or	abduction of
		starting position	starting position	DIP) joints ≥10°	thumb ≥10°
Moderate	Flexion ≥45° and	Extension ≥20°	Extension ≥10°	Extension MCP	Extension or

Abduction ≥45°	from a 90° flexed	from fully flexed	and (PIP or DIP)	abduction of
	starting position	starting position	joints of at least 2	thumb ≥10°
			fingers ≥10°	

Measurement/Instrumentation

Primary measures:

- Motor Activity Log
- Wolf Motor Function Test

Secondary measures:

- bilateral activity monitors (accelerometers)
- Patient Health Questionnaire (PHQ-9)
- Touch Test Monofilaments
- Neuro-QOL
- 9-Hole Peg Test
- Brief Kinesthesia Test
- Kinematic Analysis (performed on skeletal Kinect data collected during game play)
- Montreal Cognitive Assessment (MoCA)

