Handling missing data - We will prevent missing data through the use of checklists. These checklists will ensure that all measures are collected at each assessment session in a consistent order according to study protocol. Checklists will also minimize data loss due to technical difficulties (e.g., improper initialization of the bilateral activity monitors, dead batteries, etc.). Automated reminder calls will be sent to participants to reduce missed appointments and to remind participants to wear the activity monitors. Missed appointments will be rescheduled immediately. Testing data will be entered into a secure (and backed-up) REDCap database within 48 hours of data collection. Reasons for drop-out (and whether drop-out was therapist or participant-initiated) will be documented in detail. Loss to follow-up will be minimized by collecting multiple types of contact information and an alternate contact for the participant should he/she be unreachable.

Data Analysis- Missing data from participants who are *unable* to complete the protocol (e.g., due to random factors unrelated to the study protocol) will be removed from analysis via list-wise deletion. An *intent-to-treat analysis* will be carried out such that data from participants who *voluntarily withdraw* from treatment or are unable to tolerate the treatment protocol will be included; the mixed effects model planned for analysis is purely likelihood-based and can make use of all of the data available with no necessary modifications for differing numbers of subjects at each time point. Therapy-induced changes in motor ability (primary outcome measures of accelerometry and WMFT) will be analyzed via *mixed effects linear models*. Initially, separate models will be constructed for the two primary outcome measures. Each of these models will include treatment and time (as well as their interaction) as fixed effects and subject as a random effect. In these models, the *interaction of treatment and time is the primary effect of interest*, since it quantifies the difference in change over time among the four treatment groups. Statistical testing will be used to determine whether individuals lost to follow-up differ from those who completed the study. Demographic measures

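### The second primary outcome is contradictory: Aim 4a and the measures list name the Motor Activity Log, while Data Analysis names accelerometry and gives the Motor Activity Log no treatment-effect model

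*Combined protocol and SAP*

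**What the plan says.** Five places in the combined protocol and SAP bear on the point.

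- **I. Objectives, Aim 4a.** "The Motor Activity Log (a reliable and valid measure of arm use for daily activities) and the Wolf Motor Function Test" are the two measures named, and they "will serve as primary motor outcome measures".
- **Measurement/Instrumentation.** The MAL and WMFT stand under "Primary measures". The first entry in the secondary list is "bilateral activity monitors (accelerometers").
- **Research Design.** "Motor function (Wolf Motor Function Test) and daily use of the more affected hand (accelerometry) will be measured prior to treatment", and again after treatment and 6 months later. The MAL is not mentioned, and neither measure is called primary.
- **III. Procedures, Data Analysis.** "Therapy-induced changes in motor ability (primary outcome measures of accelerometry and WMFT) will be analyzed via" linear mixed models. The text continues: "Initially, separate models will be constructed for the two primary outcome measures". Each model has treatment, time and their interaction as fixed effects, and the interaction is the effect of main interest.
- **Opening section, "Dates of IRB Approvals and Associated Modifications".** It lists the approval of Aim 4 on 11/23/15 and three later modifications (9/20/16, 3/9/17 and 5/3/17). These concern recruitment flyers, a device risk determination and a qualitative survey.

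**The concern.** A plan should let a reader identify the primary outcomes and the model for each before any data are seen. Here the aim and the analysis disagree about one of them. The disagreement concerns arm use in daily life, which the background presents as central to CI therapy, and the two candidates measure it in different ways: one is the participant's own report, the other is instrumented.

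Two things are at stake. First, the headline arm-use result could rest on either measure, and the two could disagree. Second, while two measures compete for one primary slot, the choice could be made after comparative data are known. The Administration section plans an analysis after 50% recruitment, shares it with the site investigators, and does not say which outcomes it covers.

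**Working it through.** The plan gives no sample size, power or significance level for this point, so there is no figure to reproduce. The check is a comparison of texts.

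**Step 1. Status of each measure, by section.**

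| Section | WMFT | MAL | Accelerometry |
|---|---|---|---|
| Aim 4a | primary | primary | not named |
| Measures list | primary | primary | secondary |
| Research Design | named, no status | not named | named, no status |
| Data Analysis | primary | not named | primary |

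WMFT is consistent. The conflict is confined to the second slot.

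**Step 2. What a literal reading of Data Analysis does.** The sentence about separate models follows directly on the one that identifies the two primaries as accelerometry and WMFT. Taken literally, those two are modelled. The only other analysis wording that could reach the MAL is the general comparison of initial outcome scores between groups, which is a baseline check and not a treatment-effect analysis.

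**Step 3. Is there a tie-breaker?** No section says which text governs. None of the three later modifications touches the outcomes. The registration and published protocol are referred to, but their outcome statements are not in this document.

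**Step 4. Are the two measures interchangeable?** Each overlaps with treatment content, in different arms.

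| Arm | MAL used in treatment | Arm-movement counts used in treatment |
|---|---|---|
| Group 1 | yes: 10 treatment days + 4 follow-up calls = 14 columns on the treatment record | no smart watch |
| Groups 2 and 3 | yes: in-game MAL reviewed with problem-solving, then four weekly follow-ups | yes: smart watch, nightly log, goal set from the stronger arm |
| Group 4 | none in the usual-care materials | no smart watch |

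The activity monitors that supply the accelerometry are issued in every arm and are separate from the smart watch. The behaviour they record is nevertheless coached in Groups 2 and 3 only. The measures could therefore separate in any comparison with Group 4, and in Group 1 against Groups 2 and 3.

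**Step 5. Illustration only.** Assume a two-sided 5% level for each test, no true effect, and that whichever arm-use measure is significant is reported as primary. None of these assumptions is in the documents. The false-positive rate for arm use is then 1 − P(|Z1| < 1.96 and |Z2| < 1.96):

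- correlation 0: 1 − 0.95 × 0.95 = 0.0975
- correlation 0.5: 0.0907
- correlation 0.9: 0.0704

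For a treatment-by-time test with time as categories, the degrees of freedom are (4 − 1) × (3 − 1) = 6. If the same correlation is assumed in each component, the range is much the same: 0.0975 at correlation 0 and 0.0725 at 0.9.

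**The case against.** The strongest reply is that the parenthesis in Data Analysis is a slip. The aim and the measures list are the two places dedicated to defining outcomes, and they agree. The sentence about separate models is generic, and the same model would fit the MAL unchanged. Research Design gives no measure a status. On that reading the MAL is covered and only one word needs correcting.

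Much of this stands. A mislabel is plausible, and the statement that a declared primary goes untested holds only if Data Analysis is followed as written. But no section supplies the correction, and Research Design makes the same pairing of WMFT with accelerometry, so a slip cannot simply be presumed.

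Two stronger readings are tempting and should be set aside:

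- **That the primary outcome was switched after results were seen.** A reader might infer this from the planned 50% analysis. Nothing in the documents shows it happened, and that analysis is not tied to any outcome.
- **That the MAL is contaminated by treatment and accelerometry is the clean alternative.** The MAL is indeed treatment content in Groups 1 to 3. But movement counts are a coached target in Groups 2 and 3, so accelerometry is not free of treatment content either. The documents do not show which arm either choice would favour.

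**Conclusion.** The contradiction is real and limited to one of the two primary slots; it would be too broad to say that the primary outcomes as a whole conflict. It must be corrected because it decides which result carries the arm-use conclusion. The finding rests on the text alone and needs no assumption about intent. That the conclusion could differ with the choice follows from the different nature of the two measures and their different overlap with treatment; the size and direction of any difference are unknown. The range of about 7% to 9.75% against an assumed 5% shows what free choice between the measures could cost. It is not an estimate for this trial, and the point does not depend on it.

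**What to change.** Reconcile Aim 4a, Research Design, the measures list and Data Analysis to one arm-use primary alongside WMFT. Either direction is workable:

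- **Keep the MAL**, which matches Aim 4a and the list. Name it in Data Analysis and state which scale is the endpoint. The score sheet has Amount and How Well columns, screening uses QOM, and the treatment checklists use How Well only; the endpoint score is not stated.
- **Keep accelerometry.** State its summary variable, and change Aim 4a and the list to match.

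Fit the planned mixed model, with its treatment-by-time interaction, to the chosen measure and to WMFT. Analyse the other arm-use measure with the same model as a named secondary, and report both whatever they show.

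If comparative data have already been seen, state when the choice was made and by which role, and report both measures with that disclosure. This may already apply, since the opening section refers to a journal article on the trial.

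The cost is a wording change and one more model. The outcome schedule already places both measures at pre-treatment, post-treatment and 6 months, so no new visits, data or participants are needed.

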- You have experienced a stroke
- You still have trouble using your arm or hand
- You have at least a small amount of finger movement

Participation involves up to 35 hours of therapy and 3-4 sessions of motor testing. Enrolled participants will receive \$50 per testing visit & free access to study-related rehabilitation technologies.

Contact: Neurorecovery Lab at [contact] / [contact]

Wexner Medical Center

| Stroke Rehab Study |
|--------------------|--------------------|--------------------|--------------------|--------------------|--------------------|--------------------|--------------------|--------------------|--------------------|--------------------|
| Neurorecovery Lab |
| [contact] | [contact] | [contact] | [contact] | [contact] | [contact] | [contact] | [contact] | [contact] | [contact] | [contact] |
| | | | | | | | | | | |

S

HAVE YOU HAD A STROKE?

Would you like to participate in a research study **EXAMINING A NEW MOTOR REHABILITATION GAME?**

You may qualify if:

- You are 18 or older
- ness in your arm or and experience weak-You have had a stroke

Would you like to participate in a research study **EXAMINING A NEW MOTOR REHABILITATION GAME?**

HAVE YOU HAD A STROKE?

You may qualify if:

- You are 18 or older
- and experience weak-You have had a stroke ness in your arm or

THE OHIO STATE UNIVERSITY

HAVE YOU HAD A STROKE?

Would you like to participate in a research study **EXAMINING A NEW MOTOR REHABILITATION GAME?**

You may qualify if:

- You are 18 or older
- and experience weak-You have had a stroke hand ness in your arm or

THE OHIO STATE UNIVERSITY

WEXNER MEDICAL CENTER

WEXNER MEDICAL CENTER

HAVE YOU HAD A STROKE?

WOULD YOU LIKE TO PARTICIPATE IN A RESEARCH STUDY

You may qualify if:

- You are 18 or older
- You have had a stroke hand and experience weakness in your arm or

WEXNER MEDICAL CENTER THE OHIO STATE UNIVERSITY

Date

Dear (name),

Your [insert care provider service or name here] would like you to be aware of important research studies being conducted at The Wexner Medical Center. Researchers are looking for participants who have experienced a stroke and continue to have trouble using their weaker side. The enclosed brochure[s] describe[s] studies that are now enrolling participants.

If you are interested in participating or learning more about a study, please do one of the two following actions:

- 1. Contact us at **XXXXXX** for more information.
- 2. E-mail us at [contact]

We would like the opportunity to help you learn more about Stroke rehabilitation research at The Wexner Medical Center.

As with all research conducted at the Wexner Medical Center, your participation is voluntary. There will be no consequences to you if you choose not to participate; your medical care will not be affected by that choice. If you are eligible and choose to participate, the results of this study may help us provide better rehabilitation from stroke, and benefit individuals with stroke in the future.

Thank you in advance for considering this request

Sincerely,

Phone Screening

PATIENT INFORMATION:			
Name:			
Address:			
Phone: () D	OB: Date of C	Contact:	
	5 July 67 6		
SUPPORT PERSON INFORMATION* *other than a physician, e.g., caregiver, family	member, friend, nurse, etc.		
Name:			
Address:			
Phone: _(R	elationship:		
Do we have your permission to contact this sup	pport person regarding the study?	Y	N
Do you have reliable transportation to the med screening/testing sessions?	ical center to attend up to 4	Y	N
Are you willing to make up to 10 half-day trips the study?	s to the medical center over the cou	rse of Y	N
THE FOLLOWING QUESTIONS HELP US OLIKELY TO BENEFIT FROM CONSTRAIN			ETHER YOU ARE
Have you experienced a stroke at least 6 month	ns ago?	Y	N
If yes, date of stroke?			
Do you continue to experience difficulty moving side of your body?	ng your hand or arm on one	Y	N
Which arm/hand is weaker?		R	L
Have you ever received constraint-induced mo constraint-induced movement therapy for your		Y	N
Have you previously participated in a research project to help you regain function in your weaker arm?			N
If so, please describe:			
Are you currently taking any medications to re hand/arm (e.g., Botox)?	duce tone in your weaker	Y	N
Do you use any devices to help you move your	weaker arm/hand?	Y	N
If so please list	How long used?		

Do you have any surgeries planned in the next 3 months?	Y	N
If your weaker hand is flat on a table, can you raise it without using the shoulder or elbow?	Y	N
Please answer the following questions with your weaker forearm resting on the and hand hanging loosely over the front edge of the armrest. These questions a		
Can you bend your wrist back without lifting your forearm?	Y	N
Can you open your hand?	Y	N
Can you move your thumb away from the palm of your hand?	Y	N
Now move your arm back on the armrest so that the palm of your hand is flat o hanging loosely over the front edge of the armrest.	on the armrest and	d your fingers are
Can you lift at least two fingers while keeping your palm in contact with the armrest?	Y	N
Answer the following questions about your weaker arm. It can be placed in any perform these tasks.	v position that ma	kes it easier for you to
Can you straighten your elbow?	Y	N
Can you raise your arm at the shoulder?	Y	N
Can you pick up a tennis ball and release it?	Y	N
Can you pick up a washcloth and release it?	Y	N
PAIN SCREEN		
Do you have pain that interferes with your life or activities?	Y	N
If so, which word or words best describe the pattern of your pain?		
Continuous Periodic (sometimes present) Momen	ntary (lasting a sh	ort time)
What kinds of things relieve your pain?		
What kinds of things increase your pain?		
Please answer each of the following questions using the most appropriate rating and 10=excruciating pain		
Which rating describes it as its worst during the past week?		
Which rating describes it when it is at its least during the past week?		

Which rating describes your pain on average during the past week?

RCT In-Person Participant Screening Form

Date:	Evaluato	or	
Participant's name:			
DOB:			
Gender:			
Race:			
Contact person:			
Address:			
Phone:			
Pre-morbid handedness:			
Side of Hemiparesis:			
Date of Stroke:			
Family and Friends (Required: case we cannot get hold of the		one numbers of family and	friends ir
Name:	Relationship:	Phone:	

ALL BULLETED INCLUSION CRITERIA MUST BE MET

I. Active Movement

1. Active Wrist and Finger Extension:

Starting position: Participant's forearm on supporting surface (in pronation) with hand hanging over edge of supporting surface allowing full wrist flexion or subject's available range of motion.

Participants must be able to actively extend wrist 10° from the starting position, extend or abduct the thumb at least 10° from the starting position and extend the metacarpophlangeal and interphalangeal joints of at least 2 additional digits 10°. Picks up a washcloth from table and releases it. Must be able to perform each activity at least 3 times in 1 minute. Criteria can be met with a device such as Saebo Glove if participant is willing to use this device consistently during the trial.

- Extension of wrist: 10° or more
- Extension or abduction of thumb: 10° or more
- Extension of MCP and PIP joints at least 2 additional digits: 10° or more
- ✓ Does participant meet these criteria? Y N

2. Active Shoulder Motion

Participant must be able to actively flex and abduct shoulder to at least 45°. Note: For the purposes of this screening, the flexion may be exhibited from a position ranging from that of strict forward flexion toward scaption (which, on a horizontal plane, is half way between shoulder flexion and abduction); whereas, abduction may be exhibited from a position ranging from scaption to full abduction at the side of the body.

Starting position: participant seated in chair with a back; UE resting in subject's lap.

- Flexion of shoulder: 45° or more
- Abduction of shoulder: 45° or more
- ✓ Does participant meet these criteria? Y N

3. Active Elbow Extension

All Groups – Participant must be able to actively extend at least 20° from the 90° position. Starting position: Participant seated in chair with back; UE supported by tester in 90° of shoulder flexion (or maximal shoulder flexion possible if PROM is less than 90°) providing a gravity eliminated position for elbow extension and elbow flexed at 90°.

- Extension of elbow: 20° or more from 90° flexed position
- ✓ Does the participant meet this criterion? Y N

II. Passive ROM:

- Shoulder flexion (90 degrees or more):
- Shoulder Abduction (90 degrees or more):
- Shoulder External Rotation (45 degrees or more):
- Elbow Extension (-30 degrees contracture or less):
- Forearm Supination (45 degrees or more from neutral):
- Forearm Pronation (45 degrees or more from neutral):
- Wrist Extension (to neutral or more):
- MCP Extension (-30 degrees contracture or less):
- ✓ Does the participant meet these criteria? Y N

III. Vision/ Hearing:

Participants must have adequate vision and hearing to perform testing (with correction).

- Able to see MAL scales.
- Hear instructions for testing.
- ✓ Does the participant meet these criteria? Y N

IV. Communication - Aphasia Criteria

Participant must understand what therapist says (e.g., 1-step commands) and be able to indicate a response either verbally or through use of gesture/physical demonstration. Expressive language is not required.

- Adequate communication ability to participate fully
- ✓ Does the participant meet this criterion? Y N

V. Motor Activity Log

This criterion is most useful for identifying which participants with higher motor functioning are eligible to participate. There is no maximum level of motor ability for the study, but participants must exhibit non-use of the weaker arm (score less than 2.5 on the QOM portion of the MAL). When non-use is obvious and motor impairment is pronounced, you need not administer MAL.

- MAL QOM less than 2.5
- ✓ Does the participant meet these criteria? Y N

VI. Pain

Potential participants will be given the option to self-exclude if they have pain that would be significantly aggravated by participation in the protocol. Consider missed days in carrying out everyday tasks due to pain and excessive discomfort.

VII. Anti-Spasticity Agents:

Participants receiving Botox injections may be scheduled after 12 weeks from when the Botox injection was administered. If the participant is using other antispasticity agents such as oral Baclofen, then that information will be noted but will not used as inclusion / exclusion criteria.

• More than 12 weeks from last Botox injection at start of trial

Are you currently using Baclofen, Dantrium or any other anti-spasticity agen If so, which one?	its? Y	N	
If botox, date of last injection?			
✓ Does the participant meet these criteria? Y N			
VIII. Administer 9-hole peg test			
If participant qualifies, see whether he/she falls in higher or lower functioning growill be based on the participant's ability to complete placement of any number of peg test within the allotted time (120 seconds).			
Higher group: can place ANY number of pegs (1-9) Lower group: cannot place any pegs			
✓ Which group is the participant assigned to?			
IX: Additional Questions			
	(circle one)		
Are you able to maintain standing balance for 2 minutes; using UE for support if needed without the assistance of another person?	Y	N	
Are you able to independently and safely transfer to/from the toilet and manage clothing/hygiene?	Y	N	
Are you able to independently stand from a sitting position?	Y	N	
Do you plan to use a device during the trial (e.g., Saebo)?	Y	N	
X: Summary and Planned Follow-up:			
XI: If enrolled			
Randomization Group?			
Date of Pretest:			
Date of Post-test:			
Date of 6-month follow-up:			

Treatment materials – CI therapy

Checklist

Note: Bolded items are separate sheets within the treatment packet to be completed

Prior to Treatment (after pre-test)

- 1. Provide the activity monitors to participants and demonstrate use.
- 2. Instruct them to wear the activity monitors on both arms for 2 days before treatment to establish a baseline of arm use.
- 3. Make sure participant knows to charge them overnight every night.
- 4. Instruct participant to watch CIMT videos on YouTube. Give them the link.

Treatment Day -1 (TD 1)

- 1. Turn video camera on & show participant ID, treatment day, date, and group
- 2. Complete Treatment Received Form
- 3. Introduce the **Treatment Contract** by reading/explaining each component of the therapy. Briefly present the research.
 - discuss the need for massed practice with the weaker arm and limited use of the stronger arm to drive brain plasticity.
 - discuss how quality of life improvements relate directly to the amount of use for daily activities, regardless of motor ability.
- 4. Home Achievement Record portion of Treatment Contract.
 - Compile list of daily activities done on both weekdays and weekends (one list)
 - Photocopy daily activities list prior to categorizing level of involvement of the weaker arm in each task (10 copies). Provide 1 copy to client to complete prior to next session.
 - Discuss involvement of the weaker arm in each task with problem-solving.
- 5. **Caregiver contract**. Provide instruction to family member/caregiver on problem-solving approach. ("You'll notice that I used a particular approach to help clients come up with solutions to some of the barriers to using the weaker arm.")
 - "Say" They come up with a plan. No questioning.
 - "Do" They try it out
 - "Check" To note what worked and what didn't. Revise the plan.
- 6. Ask participant if he/she watched the CIMT videos on YouTube. If they have not yet, assign as homework.
- 7. Ask participant about adverse events during previous session(s) and fill out **Adverse Event Reporting Form** if need be
- 8. Donn the mitt

- 9. Perform ~9 shaping tasks—document on **Task List**, **Shaping Data Sheets**, and **Shaping Graphs** (1 per task)
- Administer the full MAL-all 28 items using the How Well Scale only (add to MAL spreadsheet)
- 11. Turn video camera off and add comments to **Therapist Treatment Recording Log**
- 12. Store the video on the encrypted hard drive under the correct group and session subfolder

Treatment Day- 2 (TD 2)

- 1. Turn video camera on & say participant ID, treatment day, and group
- 2. Check the mitt time and record it on the Task List; donn the mitt. If mitt wear time is low, problem-solve compliance as needed.
- Administer a half MAL using the How Well Scale only (record responses on MAL spreadsheet)
- 4. Review the Home Achievement Record with the patient
- 5. Perform ~9 additional shaping tasks (different from those on TD 1)—document on **Task List, Shaping Data Sheets**, and **Shaping Graphs** (1 per task)
- 6. Explain the Home Skill Assignment List (HSA) and select the 10 items
- 7. Give the patient the next Home Achievement Record form
- 8. Ask participant about adverse events and fill out **Adverse Event Reporting Form** if need be
- Turn video camera off and add comments to Therapist Treatment Recording Log
 Store the video on the encrypted hard drive under the correct group and session subfolder
- 11. Ask participant if he/she watched the CIMT videos on YouTube. If they have not yet, assign as homework.

Treatment Day- 3 (TD 3-5, 7-10)

- 1. Turn video camera on & say participant ID, treatment day, and group
- 2. Check the mitt time and record it on the Task List; donn the mitt. If mitt wear time is low, problem-solve compliance as needed.
- Administer a half MAL using the How Well Scale only (record responses on MAL spreadsheet)
- 4. Review the HSA
- 5. Review the Home Achievement Record with the patient
- 6. Repeat the 9 shaping tasks from TD1/TD2 (alternating between treatment days); can now consider shaping the tasks –document on Task List, Shaping Data Sheets and Shaping Graphs
- 7. Select the 10 items for the Home Skill Assignment (HSA) list
- 8. Give the patient the next **Home Achievement Record** form

- 9. Ask participant about adverse events and fill out **Adverse Event Reporting Form** if need be
- 10. Ask participant if he/she watched the CIMT videos on YouTube. If they have not yet, assign as homework.
- 11. Turn video camera off and add comments to **Therapist Treatment Recording Log**
- 12. Store the video on the encrypted hard drive under the correct group and session subfolder

Treatment Day- 6 (TD 6)

- 1. Turn video camera on & say participant ID, treatment day, and group
- 2. Check the mitt and record it on the Task List; donn the mitt. If mitt wear time is low, problem-solve compliance as needed.
- 3. Administer a full MAL all 28 items using the How Well Scale only (record responses on **MAL spreadsheet**)
- 4. Review the HSA
- 5. Review the weekend Home Achievement Record with the patient
- 6. Repeat the 9 shaping tasks from TD2; can now consider shaping the tasks—document on **Task List**, **Shaping Data Sheets** and **Shaping Graphs**
- 7. Select the 10 items for the Home Skill Assignment (HSA) list
- 8. Give the patient the next Home Achievement Record form
- 9. Ask participant about adverse events and fill out **Adverse Event Reporting Form** if need be
- 10. Ask participant if he/she watched the CIMT videos on YouTube. If they have not yet, assign as homework.
- 11. Turn video camera off and add comments to **Therapist Treatment Recording Log**
- 12. Store the video on the encrypted hard drive under the correct group and session subfolder

How to reset mitt device

- 1. Unscrew 4 outer edge corners (Red Arrows)
- 2. Hold down black button for ~5 seconds (Blue Arrow)
- 3. Re-screw 4 outer edge corners

MAL in follow-up
MAL How Well administered with problem solving weekly for 1st month via phone. 20 min. each. (4 times total)

• Record responses on MAL spreadsheet

Description of Therapy

Constraint Induced Movement Therapy or CI therapy is thought to work because it has been shown to produce a large "rewiring" of the brain; that is, after treatment, a larger part of the brain is involved in producing movement of the weaker arm than before therapy. It also has the effect of overcoming a strong tendency not to use the weaker arm ("learned nonuse") that develops in the early post-stroke period.

Research has shown that patients can "learn" to improve the motor ability of the weaker parts of their bodies and thus cease to rely exclusively or primarily on the stronger parts. For this learning and rewiring to occur, two things have to happen:

- 1. Intensive training of the weaker arm in the clinic. This will occur through intensive training of the weaker arm and hand in the laboratory for 3 hours a day for 10 days.
- 2. Use of the weaker arm for daily activities (more than the stronger arm) OUTSIDE the clinic. This is linked to structural changes in the brain and improved quality of life. Research has shown that these improvements are absent when improved motor function does not carry over to daily life. Three things will help you carry-over in-lab improvements to your daily activities.
 - a. Restraint of the stronger arm in a **padded mitt** for a large number of waking hours over the treatment period in the laboratory and at home.
